8. STUDY SUBJECT DATA

8.1. Subject Disposition

Summaries of analysis population membership, final subject status (completed or withdrawn), including reasons for withdrawal, sub study participation, and study duration in days will be produced based on the number of randomized subjects. The number of subjects screened will be provided. Data will be presented by treatment group as well as overall for the study, with exception of the number of screen failures (to be displayed without respect to treatment).

Screen failures, analysis populations, and final subject disposition status will be listed.

8.2. Protocol Deviations

Protocol deviations will be identified and classified as important or not important. Important protocol deviations may include but are not limited to:

- Violation of Inclusion/Exclusion Criteria
- Study drug compliance $\leq 80\%$ or $\geq 120\%$
- Use of prohibited therapies
- Incorrect treatment

Protocol deviations including category will be summarized by treatment group and overall for the study. Protocol deviations due to COVID impact will be identified as such.

A listing of all protocol deviations will be provided.

8.3. Demographic and Baseline Characteristics

Subject demographics and baseline characteristics will be summarized and listed. Data will be presented by treatment group as well as overall for the study.

Demographic and baseline characteristics summaries will be provided for the ITT population, mITT population, safety population, and Serial PK population.

8.4. NASH History

Subject NASH history will be summarized and listed. Days since biopsy, fibrosis stage, NAS, Steatosis score, ballooning degeneration score, lobular inflammation score, Fibrosis-4 (FIB-4) Score, and MRI-PDFF.

NASH history summaries will be provided for the ITT population, mITT population, safety population, Serial PK population. NASH history will also be summarized for T2DM vs not T2DM.

NASH confirmation data collected at screening will be presented in a data listing.

8.5. Medical History

Medical history will be coded using the Medical Dictionary for Regulatory Activities (MedDRA) version 24.0 or higher for reporting by system organ class (SOC) and preferred term (PT). Medical history data will be presented in a listing.

8.6. Prior and Concomitant Medication

The incidence of medication use will be summarized by WHO Drug Dictionary, Global B3 Mar2021 or higher, anatomic therapeutic class (ATC) Level 2 classification (i.e., therapeutic main group) and preferred name. A subject will be counted only once at each level of reporting. Prior medications are medications that have been discontinued prior to the treatment start date (e.g., taken exclusively during the pre-therapy period). Concomitant medications are medications taken at any point during the on-therapy or post-therapy periods. Subjects could start a concomitant medication prior to study start which is ongoing at time of first treatment or subjects could start a new medication during the on-therapy or post-therapy periods.

Concomitant medication use will be summarized separately and presented by treatment group for the ITT population.

All prior and concomitant medication data will be listed including the verbatim and preferred drug name and ATC Level 2.

8.7. Study Drug Exposure and Compliance

Duration of drug exposure will be summarized both as a continuous and a categorical variable for the safety population. Exposure will be calculated as:

study drug stop date – study drug start date + 1 [converted to weeks (days divided by 7)]

Categories for reporting exposure will include < 13 weeks; 13 weeks - < 26 weeks; 26 weeks - <39 weeks; 39 weeks - < 52 weeks; \geq 52 weeks.

Drug accountability is captured in the eCRF at each visit. The eCRF captures the number of pills returned and the number missed during the dosing period. Overall compliance will be determined based on pill counts over each visit period and taking into account the number missed.

Compliance will be derived as:

$$\frac{[(\# \text{ of pills dispensed} - \# \text{ of pills returned}) - \# \text{ of missed pills}] \times 100}{2 \times (\text{number of days within the visit period})}$$

Where number of days within the visit period is derived as:

$$\text{Date of Visit (X+1)} - \text{Date of Visit (X)} + 1$$

Compliance will also be summarized for the following categories < 80%, 80% - 120%, and > 120%.

Mean daily dose (mg) and total cumulative dose (mg) received will also be summarized. Total cumulative dose will be summarized overall and separately for those that had extended dosing.

Listings of planned and actual treatments, overall compliance, and drug exposure will be produced.

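### The SAP compliance formula counts interior visit days twice and, if missed pills also come back in the bottle, subtracts those pills twice

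*SAP*

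**What the plan says.** SAP Section 8.7 says of the data that "The eCRF captures the number of pills returned and the number missed during the dosing period", and of the method that "Overall compliance will be determined based on pill counts over each visit period and taking into account the number missed". For each visit period the formula is:

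- numerator: (dispensed − returned) − missed, times 100;
- denominator: 2 × days in the period;
- days: date of the next visit − date of this visit + 1.

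The SAP does not define *missed* and does not say whether a missed pill can also be among the returned pills.

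The result is used in two places. Section 8.7 says: "Compliance will also be summarized for the following categories < 80%, 80% - 120%, and > 120" (per cent). Section 8.2 gives "Study drug compliance" at or below 80%, or at or above 120%, as an example of what may be an important protocol deviation.

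Three protocol sections bear on the formula. Section 9.5 has every subject take two tablets once daily in the evening. Section 9.8 has subjects bring the diary and the containers to each visit, and counts returned material as one check of compliance. Section 7.1 sets visits at Weeks 4, 8, 13, 26, 39 and 52.

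**The concern.** There are two separate problems.

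**Day count.** Adding one is right for a single closed interval, such as the exposure duration defined in the same SAP section. It is not right for consecutive periods that share a boundary date. With one evening dose per day, the dose on a visit date belongs to one period only, but the formula expects it in both.

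**Numerator.** Dispensed minus returned already leaves out any untaken pill that comes back in the bottle. If that pill is also recorded as missed, it is removed again. Each subject's shortfall from full compliance is then doubled, and so is any difference in shortfall between the arms.

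At stake are the reported compliance figures, the split around 80%, and which subjects may be labelled as important deviators in the study report.

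**Working it through.** The SAP gives a formula and limits but no compliance result, so there is no stated figure to reproduce. The formula can be applied directly.

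**Inputs.** Two tablets per day (Protocol 9.5, SAP 8.7). Period length D from the visit schedule (Protocol 7.1): 28, 28, 35, 91, 91 and 91 days, 364 in all. True compliance c is an assumption, since the documents give none; 90% is used as the example. The share r of missed pills that are returned is also unknown and is varied from 0 to 1.

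**Formula.** Pills due = 2D, taken = 2Dc, untaken = 2D(1 − c). Surplus tablets dispensed and returned cancel. If every untaken pill is recorded as missed, then

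SAP compliance = [1 − (1 + r)(1 − c)] × D/(D + 1).

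With r = 1 this is (2c − 1) × D/(D + 1). With r = 0 it is c × D/(D + 1), which is also the result if *missed* means only pills neither taken nor returned.

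**Day count alone, full compliance.** Nothing is missed, so the definition of *missed* does not matter.

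- 91 days: 182/184 = 98.9%, a loss of 1/92 = 1.1%.
- 28 days: 56/58 = 96.6%, a loss of 1/29 = 3.4%.

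**Both features, true compliance 90%, all missed pills returned.**

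- 91 days: due 182, taken 163.8, missed 18.2. (163.8 − 18.2)/184 = 145.6/184 = 79.1%.
- 28 days: due 56, taken 50.4, missed 5.6. (50.4 − 5.6)/58 = 44.8/58 = 77.2%.

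**Dependence on the share returned, true compliance 90%.**

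| Missed pills returned | 28 days | 91 days |
|---|---|---|
| All (r = 1) | 77.2% | 79.1% |
| Half (r = 0.5) | 0.85 × 28/29 = 82.1% | 0.85 × 91/92 = 84.1% |
| None (r = 0) | 0.90 × 28/29 = 86.9% | 0.90 × 91/92 = 89.0% |

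**Each feature alone at 90%.** Double subtraction without the plus one gives exactly 80.0%. The plus one without double subtraction gives the last row of the table.

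**Where the 80% limit falls if r = 1.** Solving (2c − 1) × D/(D + 1) = 0.80 gives c = [0.80 × (D + 1)/D + 1]/2, which is 90.4% at 91 days and 91.4% at 28 days.

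**Over 52 weeks, summing the periods.** Pills due are 2 × 364 = 728. The denominator is 2 × (364 + 4) = 736 with four 91-day periods, or 2 × (364 + 6) = 740 with the six visit periods. Full compliance gives 98.9% or 98.4%. A true 90% with r = 1 has numerator 0.80 × 728 = 582.4, giving 79.1% or 78.7%.

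**After correction.** Without the plus one and the second subtraction, 90% computes as 90.0% and full compliance as 100%, for any D.

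**The case against.** The strongest reply is that the double subtraction is not established. The SAP treats returned and missed as two eCRF counts, and the form and its completion guidelines are not among the documents. If the field holds only pills neither taken nor returned, the numerator is correct. Protocol 9.8 says that containers come back; it does not say how the missed field is filled. This stands. A reader might infer that 90% compliance will be reported as below 80%. The documents do not support that without the condition that essentially all missed pills are in the returned count, because with half returned the figure stays above 80%. Even with all returned, double subtraction alone only reaches 80.0%, and the plus one takes it lower.

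The period length is also open. SAP 8.7 and Protocol 9.8 refer to each visit, but the marks for dispensing and accountability in the Schedule of Assessments may point to roughly 91-day periods. The column headings did not survive in the text available, so the 28-day figures are conditional.

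The day-count loss is small at about 1.1% to 3.4%, and a fully compliant subject stays far from any limit. That is fair as to size, but the rule still returns a wrong number on any reading of *missed*.

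A reader might also infer damage to the efficacy results. The documents do not support that. No analysis population in SAP Section 6 uses compliance, and the principal analysis is on all randomized subjects. The 50%, 70% and 80% dose subsets in Section 9.1.2 are set in milligrams of cumulative dose, and the SAP does not tie them to this formula. Nor is deviation flagging automatic: Section 8.2 says only what important deviations may include.

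**Conclusion.** The concern holds in two parts of different certainty.

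The day count is wrong as written. It lowers every period's compliance by about 1.1% (91 days) to 3.4% (28 days) in relative terms, given one evening dose per day and D doses due between visits D days apart.

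The numerator is wrong on the ordinary reading, in which an untaken pill comes back in the bottle and is also recorded as missed. Together with the day count, a true 90% then computes as about 79% over 91 days, or 77% if periods are 28 days, and the 80% limit acts at a true compliance of about 90% to 91%. Because *missed* is undefined, this part is conditional.

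The consequence is limited to the compliance summaries and listings, the below-80% category and a possible important-deviation label. It is worth correcting because the reported numbers would be wrong and the correction is simple, but it does not threaten the principal efficacy analysis.

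**What to change.** In SAP Section 8.7:

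1. Define the days in a visit period as the date of the next visit minus the date of this visit, without adding one.
2. Use dispensed − returned − pills neither taken nor returned as the numerator, and state that missed doses already in the returned count are not subtracted again.
3. Define *missed* by reference to the eCRF completion guidelines. If the field records every missed dose, wherever the pill went, leave it out of the numerator and report it separately as a cross-check.
4. Apply the corrected figure to the 80% and 120% limits in Sections 8.2 and 8.7, and align the two sections on how exactly 80% and exactly 120% are classed.
5. State whether the cumulative dose in Sections 8.7 and 9.1.2 is derived from the same pill counts.

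The cost is a text and programming edit with no new data collection. SAP Section 2 requires the approved version to precede unblinding. Making the change by then avoids reclassifying deviations after treatment is known.

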9. EFFICACY

9.1. Primary Efficacy Endpoint Analyses

9.1.1. Principal Analysis of the Primary Efficacy Endpoints

The principal efficacy analyses will be conducted on the ITT population. Additional sensitivity and supplementary analyses will be performed for the primary efficacy endpoints, as described in the next section.

The treatment groups will be compared based on the primary efficacy endpoints using one-sided Cochran-Mantel-Haenszel (CMH) tests stratified by the randomization stratifications T2DM status at baseline (yes or no) and amount of fibrosis at baseline (F2 or F3).

Mathematically, the null and alternative hypotheses for the primary efficacy endpoints are stated as:

$$H_0: p_T \leq p_p$$

$$H_a: p_T > p_p$$

Where, p_T is the proportion of responders in the TVB-2640 50-mg treatment group and p_p is the proportion of responders in the placebo treatment group. The higher responder proportion is a better outcome.

A Clopper-Pearson 90% and 95% CI will be derived for each treatment group, and the stratified CMH odds ratio (with its 90% and 95% CI, using the control group as a reference group) will be produced to assess the treatment effect magnitude. The difference in treatment groups response rates will be provided and also be characterized by the 90% and 95% CIs using Miettinen and Nurminen (1985).

Subgroup analyses of the primary efficacy endpoints will be performed to assess whether the treatment effect is concordant among subgroups. The planned subgroup analyses are described in Section 7.2. Analyses will be performed if there is an adequate number of subjects in each subgroup.

A subject who discontinues treatment prior to Week 42, does not provide a histological assessment on or after Week 42, or who otherwise has missing data will be considered a non-responder.

9.1.2. Sensitivity Analyses of the Primary Efficacy Endpoints

Evaluation of the robustness of the principal analysis of the primary efficacy endpoints will be carried out using the following (4) four approaches:

- A logistic regression with response as a dependent variable; treatment group, randomization stratification factors (T2DM status at baseline [yes or no] and amount of fibrosis at baseline [F2 or F3]) as independent factors; and age as a baseline covariate.
- The analysis of the primary efficacy endpoints will be repeated for the modified Intention-to-Treat (mITT) population to ascertain any changes in the conclusion of the principal analysis findings.
- A repeat of the primary efficacy analysis principal analysis (CMH test) for the following three ITT subsets:
 - ITT Subjects who achieve at least 50% of total cumulative study drug dose (i.e., at least **9100 mg** 52-week total dose (based on a total of 50 mg.kg x 52 weeks x 7 days = 18200 mg x weeks x days).
 - ITT Subjects who achieve at least 70% of total cumulative study drug dose (i.e., at least **12740 mg** 52-week total dose (based on a total of 50 mg x 52 weeks x 7 days = 18200 mg x weeks x days).
 - ITT Subjects who achieve at least 80% of total cumulative study drug dose (i.e., at least **14560 mg** 52-week total dose (based on a total of 50 mg.kg x 52 weeks x 7 days = 18200 mg x weeks x days).
- To assess the impact of missing data in the primary endpoint analyses, multiple imputation procedure will be carried out using MAR assumption with Fully Conditional Specification method for binary endpoint in SAS PROC MI. 100 imputations will be performed. The CMH test statistic from each imputed dataset will be based on Wilson-Hilferty transformation (Wilson & Hilferty, 1931) and will be combined using PROC MIANALYZE. Combined CMH test statistic and p-value will be computed. The method described in Ratitch, Lipkovich, and O'Kelly (2013) will be used to combine the results.

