4.3. Sample Size Considerations

The study is powered to test the one-sided (statistical) superiority hypothesis stipulating that a TVB-2640 50-mg dose provides better benefit than placebo based on the primary efficacy endpoint. The study estimated total sample size is approximately 162 randomized subjects (108 on TVB-2640 and 54 on placebo). The sample size was derived using the normal approximation to the binomial distribution, and the estimated power to detect a difference in the primary efficacy response of 20% (TVB-2640 40% and placebo 20% at Week 52) was at least 80% (one-sided test at the 0.05 significance level). A 2-to-1 randomization allocation was assumed (TVB-2640 to placebo), and an anticipated dropout rate of 18.5% was also applied to estimate the final total sample size (N=162).

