7. GENERAL DATA HANDLING CONSIDERATIONS

All analyses will be conducted using SAS software Version 9.4 or higher.

All data in the database will be presented in by-subject data listings. Unless otherwise stated, all listings will be sorted by treatment group, center ID, subject number, and assessment date and time, if available.

Unless stated otherwise, continuous data will be summarized by treatment group using descriptive statistics including number of subjects (n), mean, median, standard deviation (SD), first quartile (Q1), third quartile (Q3), minimum (min) value, maximum (max) value.

Unless stated otherwise, categorical data will be summarized by treatment group using counts and percentage based on the number of non-missing values. For selected summaries, the number of missing values will be presented as a separate category with no percentage, if one or more subjects have missing data. Counts of zero will be presented without percentages.

Descriptive statistics will be presented with the following numerical precision:

- Minimum and Maximum: same as the raw data collected
- Mean, Median, Q1, and Q3: one additional decimal place to that reported for Minimum and Maximum
- SD: two additional decimal places than the Minimum and Maximum
- Percentages: reported to one decimal place if percent is <100. If the value is 100, no decimal place will be reported.

Unless otherwise noted, statistical inference will be based on two-sided testing with a 5% significance level. Confidence intervals will be at the 90% and 95% levels.

P-values will be reported to four decimal places. If the value is below 0.0001 it will be noted as < 0.0001; if the value above 0.9999 it will be noted as > 0.9999.

All data up to the time of study completion/withdrawal from the study will be included in the analysis, regardless of duration of treatment.

Numbering for data displays will be based on [International Council for Harmonization \(ICH\) E3](#) whenever possible.

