7.3. Multiple Comparisons and Multiplicity

The study co-primary hypotheses are the (statistical) one-sided superiority of a TVB-2640 50-mg dose over placebo based on each of the two co-primary efficacy endpoints at the 0.05 significance level, where a higher responder proportion is a better outcome. The statistical analysis (one-sided) test (CMH) of the primary hypothesis is declared if $p < 0.05$. No adjustment for the two co-primary efficacy tests will be performed, both will be tested at the 0.05 level using one-sided tests.

Both one-sided and two-sided 0.05 significance level tests will be used for the efficacy endpoints. The table below specifies whether the test of significance is one- or two-sided along with the expected direction of effect. No other control for multiplicity will be provided.

Note that endpoints that are being tested as one-sided will also have the two-sided p-values provided. Both 90% and 95% two-sided confidence intervals will be shown.

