7.4. Efficacy Endpoints: 1-sided and 2-sided Testing Allocation

Endpoint Number	Endpoint Description	1-sided or 2-sided	Directionality for better outcome for 1-sided tests
	Co-Primary Efficacy Endpoints		
1A	Proportion of subjects experiencing histological improvement at Week 52 in NAS (i.e., ≥ 2 points improvement in NAS with ≥ 1 point improvement in ballooning or inflammation) and without worsening of fibrosis (by NASH CRN fibrosis score)	1-sided	Higher
1B	Proportion of subjects experiencing both of the following at Week 52: 
○ Resolution of steatohepatitis and no worsening of liver fibrosis (by NASH CRN fibrosis score). Resolution of steatohepatitis is defined as absence of fatty liver disease or isolated or simple steatosis without steatohepatitis and a NAS of 0 or 1 for inflammation, 0 for ballooning, and any value for steatosis.	1-sided	Higher

Endpoint Number	Endpoint Description	1-sided or 2-sided	Directionality for better outcome for 1-sided tests
	AND 
 ○ Histological improvement in NAS (≥ 2 points improvement in NAS). 		
	Secondary Efficacy and Pharmacodynamic Endpoints		
2	Proportion of MRI-PDFF $\geq 30\%$ responders at Week 26, where an MRI-PDFF $\geq 30\%$ responder is defined as a subject with $\geq 8\%$ liver fat content at Baseline who achieves a relative reduction from Baseline in MRI-PDFF $\geq 30\%$.	2-sided	
3	Proportion of MRI-PDFF $\geq 30\%$ responders at Week 52, where an MRI-PDFF $\geq 30\%$ responder is defined as a subject with $\geq 8\%$ liver fat content at Baseline who achieves a relative reduction from Baseline in MRI-PDFF $\geq 30\%$.	2-sided	
4	Proportion of MRI-PDFF $\geq 50\%$ responders at Week 52, where an MRI-PDFF $\geq 50\%$ responder is defined as a subject with $\geq 8\%$ liver fat content at Baseline who achieves a relative reduction from Baseline in MRI-PDFF $\geq 50\%$.	2-sided	
5	Proportion of subjects with improvement in liver fibrosis ≥ 1 stage by NASH CRN fibrosis score without worsening of steatohepatitis (defined as no increase in NAS for ballooning, inflammation, or steatosis) at Week 52.	1-sided	Higher
6	Proportion of subjects with improvement in liver fibrosis ≥ 1 stage by NASH CRN score without increase of total NAS score at Week 52.	1-sided	Higher
7	Proportion of subjects with improvement in liver fibrosis ≥ 1 stage by NASH CRN score without any worsening of NASH (defined as no worsening of ballooning and lobular	1-sided	Higher

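### The multiple-imputation check in SAP 9.1.2 pools a directionless chi-square and plans no effect estimate, so it does not test the one-sided 0.05 decision (lesser point: the mg-based dose subsets have no placebo rule)

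*SAP*

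**What the plan says.** SAP 9.1.1 compares the arms on each co-primary endpoint "using one-sided Cochran-Mantel-Haenszel (CMH) tests", with the alternative that the TVB-2640 response rate is the higher one. SAP 7.3 sets the level at 0.05 for each endpoint. SAP 7.4 lists both as one-sided, in a table that has a column headed "Directionality for better outcome for 1-sided tests". The principal analysis also reports a stratified odds ratio and a difference in rates, each with 90% and 95% CIs.

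SAP 9.1.2 lists four robustness checks. The missing-data check imputes 100 times under missing at random. It continues: "The CMH test statistic from each imputed dataset will be based on Wilson-Hilferty transformation", pools with PROC MIANALYZE, and ends: "Combined CMH test statistic and p-value will be computed". It refers to a cited paper for the combining method. It names no tail, no threshold, no direction, no pooled effect and no CI.

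Two general provisions bear on the reading. SAP 7 says: "Unless otherwise noted, statistical inference will be based on two-sided testing with a 5% significance level". SAP 7.3 adds: "Note that endpoints that are being tested as one-sided will also have the two-sided p-values provided".

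Another check repeats the CMH test in three subsets, for example "ITT Subjects who achieve at least 80% of total cumulative study drug dose". The cut-offs are 9100, 12740 and 14560 mg over 52 weeks, derived from the 50 mg regimen. Neither SAP 9.1.2 nor SAP 8.7 says how placebo tablets count. Protocol 9.5 moves an adjusted active subject to a 25-mg tablet plus a placebo tablet matching the 50-mg one, and leaves an adjusted placebo subject's tablets as they were.

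**The concern.** The Wilson-Hilferty (WH) transformation is applied to a chi-square, that is, to the square of the signed CMH statistic. The sign is lost before pooling. The result is close to a two-sided p-value, whereas the trial's claim rests on a one-sided one. A reader who sets the pooled p-value beside the primary result and reads both at 0.05 may conclude that a win is not robust to missing data when only the number of sides differs. The size of the effect under imputation, which is what a missing-data check should chiefly show, is not planned to be reported. With a planned dropout of 18.5% this check will be looked at.

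In the dose subsets, a cut-off in mg of active drug has no defined meaning for placebo subjects, yet the CMH test needs both arms.

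**Working it through.** **Plan's own figures.** Unpooled normal approximation, one-sided 0.05, 80% power, 2:1, 40% vs 20%: placebo n = (1.645 + 0.842)² × (0.16 + 0.24/2)/0.20² = 43.3, so 44 + 88 = 132, and 132/0.815 = 162. Dose: 50 × 364 = 18200 mg, and 50/70/80% of it is 9100/12740/14560 mg. All reproduce.

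**WH statistic.** For a 1-df chi-square c = z², w = (c^(1/3) − 7/9)/√(2/9). Upper-tail normal p (assumed tail), no missing data:

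| signed CMH z | one-sided p | WH p |
|---|---|---|
| +1.645 | 0.050 | 0.096 |
| +1.96 | 0.025 | 0.047 |
| +2.2 | 0.014 | 0.026 |
| −2.2 | 0.986 | 0.026 |

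WH p = 0.05 needs c = (7/9 + 1.645 × √(2/9))³ = 3.747, so |z| = 1.936, a one-sided p of 0.026. If the pooled value were instead read two-tailed on the WH scale, a one-sided 0.050 would become about 0.19.

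**No missing data** (400,000 simulated trials, 108:54, four near-equal strata, 40% vs 20%). One-sided win: 84.0%. Win with WH p ≥ 0.05: 8.7%. Win with ordinary two-sided p ≥ 0.05: 9.6%.

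**With missing data** (30,000 trials per setting). Inputs from the plan: 108:54, 40% vs 20%, 100 imputations, missing counted as non-response in the primary test, and 18.5% missing because "an anticipated dropout rate of 18.5% was also applied to estimate the final total sample size". Assumed: 40% and 20% apply to assessed subjects, missingness is random and equal in the arms, four near-equal strata, imputation by arm from beta draws. WH values are pooled with total variance 1 + (1 + 1/100)B, where B is the between-imputation variance. The Mantel-Haenszel (MH) log odds ratio is pooled by Rubin's rules. At 18.5% missing the one-sided primary test wins in 73.3% of trials.

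| share of all trials | 18.5% missing | 10% missing |
|---|---|---|
| one-sided win, pooled WH p ≥ 0.05 | 8.8% | 8.4% |
| one-sided win, pooled MH one-sided p ≥ 0.05 | 2.8% | 2.0% |
| one-sided win, pooled MH two-sided p ≥ 0.05 | 10.9% | 10.2% |
| one-sided win, not (WH p < 0.10 and effect favourable) | 2.3% | 1.6% |

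Like for like, a two-sided primary p < 0.05 is followed by WH p ≥ 0.05 in 2.3% of trials (18.5% missing). At 20% vs 20%, WH p < 0.05 occurs in 5.2%, and 2.7 of those points favour placebo.

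**Dose subsets.** Counted as mg of TVB-2640, placebo subjects have 0 mg, the placebo arm of every subset is empty and the test cannot be run. If instead placebo is credited with 50 mg/day and active subjects with what they received, a fully adherent subject adjusted to 25 mg at week x has 350x + 175(52 − x) mg. Setting this to 12740 gives x = 3640/175 = 20.8. Setting it to 14560 gives x = 5460/175 = 31.2. Adjustment before those weeks removes an active subject from the 70% or 80% set, while a placebo subject with a sham adjustment stays. The 50% set is met even at x = 0, since 175 × 52 = 9100.

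**The case against.** The best defence is that the SAP supplies the reading. Inference is two-sided unless noted, SAP 9.1.2 notes nothing else, and a two-sided primary p-value will be printed. Compared that way, discordance is about 2%. This stands, and it limits the point to the match with the one-sided decision.

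A reader might infer that the WH transformation is itself defective. The figures do not support that: an ordinary two-sided p-value shows slightly more apparent failures (9.6% against 8.7%), and a pooled MH odds ratio read two-sided shows 10.9%. The cause is the number of sides. A stated rule (p < 0.10 with favourable direction) also closes the gap, although it gives no effect size.

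A reader might also infer that the check could give false reassurance. With favourable response rates, WH p < 0.05 supports the one-sided decision conservatively. If the effect favours placebo, the primary test has already failed and there is no claim to reassure. Nor is direction lost from the report as a whole: the mITT repeat carries the odds ratio and difference with CIs, and the logistic regression gives a signed effect. Neither is an estimate under imputation. The cited combining paper was not available, so it may add a directional step; the SAP states none.

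On the subsets, a reader might infer a demonstrated bias of some size. The documents give neither the frequency of dose adjustment nor the response of adjusted subjects, so none can be derived. The asymmetry also depends on the counting rule: with every tablet counted at its matched strength, each arm takes 75 mg/day before and after adjustment, and it vanishes. A set based on drug received may properly drop subjects who received less. Because the cut-offs are described as 52-week totals, doses from extended dosing appear to be left out.

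**Conclusion.** The point holds, within limits. As written, the imputation check yields a p-value without direction, roughly two-sided if the upper tail is used. It therefore does not test the one-sided 0.05 decision of SAP 7.3 and 9.1.1, and no effect size under imputation is planned. Read at 0.05 beside a one-sided win, it would appear to contradict that win in 8.8% of trials at the planning rates and dropout, against 2.8% for a one-sided pooled odds ratio; beside the two-sided primary p-value the figure is 2.3%. These percentages rest on the simulation assumptions listed above. The loss is confined to this check: the principal ITT test and N = 162 are unaffected.

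The subset rule is a smaller matter of definition: either an empty placebo arm or a counting convention that the SAP does not state. The figure of 50 mg.kg in two of the three subset bullets, beside 50 mg in the third, is clerical and must be reconciled; the cut-offs are arithmetically correct.

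**What to change.** In SAP 9.1.2, replace the pooled statistic by the stratified Mantel-Haenszel log odds ratio (or risk difference) and its standard error, combined by Rubin's rules over the 100 imputations. Report the pooled estimate, 90% and 95% CIs and the one-sided p-value. The WH p-value may stay as a supplement if the tail is stated and it is compared with the two-sided primary p-value.

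For the subsets, define membership in both arms as tablets taken as a share of tablets planned over 52 weeks, from the pill counts in SAP 8.7, and state that this is an adherence set. Reconcile the two dose units.

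The cost is SAP wording and a few lines of SAS. The imputed datasets and pill counts are already planned, and no new data are needed. The change should be made before unblinding.
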